10.3. Adverse Events of Interest (AEOI)

10.3.1. Abnormal Liver Function Test Results

Abnormal liver function tests that meet the below criteria will be considered AEOIs and must be reported to the Sponsor's Medical Monitor within 24 hours of awareness if one of the following conditions are met:

- The abnormality represents a new elevation in ALT or AST >3 times the upper limit of normal (ULN), with or without an elevation of total serum bilirubin >2 times ULN; or
- The abnormality represents a 2-fold increase in ALT or AST above the baseline value for the double-blind period (ie, Day 1) in patients who had elevated values prior to starting study medication, or a 2-fold increase in ALT or AST above the baseline value for the open-label extension (ie, Week 112) in patients who had elevated values prior to starting open-label sparsentan.

In such instances, the following steps should be taken:

1. Temporarily discontinue study medication.
2. Perform repeat testing of ALT, AST, and total bilirubin, and test liver alkaline phosphatase isoenzyme within 48 to 72 hours to confirm the abnormalities.
3. If the abnormality is confirmed by repeat results:
 - a. Complete an AEOI Report Form that documents both the liver function test findings and any associated signs or symptoms and report by email to the SAE contact on the [Study Contact Information](#) page of this protocol.
 - b. Monitor liver enzymes and serum bilirubin 2 or 3 times weekly. The frequency of re-testing can decrease to once weekly or less if the abnormalities stabilize and the patient is asymptomatic.

- c. Perform additional testing to evaluate liver function, as appropriate (eg, international normalized ratio [INR], direct bilirubin).
4. Do not resume study medication until monitoring indicates abnormalities have resolved or stabilized.

Patients are not allowed to resume study medication if they have:

- ALT or AST >8 times ULN
- ALT or AST >5 times ULN for more than 2 weeks
- ALT or AST >3 times ULN and total bilirubin >2 times ULN or INR >1.5
- ALT or AST >3 times ULN with symptoms of fatigue, nausea, vomiting, right upper quadrant pain or tenderness, fever, rash and/or eosinophilia (>5% eosinophils)

Additionally, patients who demonstrate elevated liver enzymes a second time after re-introduction of the study medication may continue in the clinical trial; however, they will not receive study medication for the remainder of the trial.

Management of such patients should be closely coordinated with the Sponsor's Medical Monitor. In addition to monitoring liver function tests, the Investigator should perform other relevant clinical and laboratory measurements to identify potential causes of the abnormalities (eg, acute viral hepatitis types A, B, C, D, and E; autoimmune or alcoholic hepatitis; non-alcoholic steatohepatitis; biliary tract disease or exposure to hepatotoxic medications or environmental chemical agents).

Cases of increased liver function tests will always be considered serious (ie, medically important) if they meet both the following criteria:

- Study medication is suspected to have caused hepatocellular injury, generally shown by a confirmed elevation of 3-fold or greater above ULN in ALT or AST; and
- The ALT or AST elevations are accompanied by a total bilirubin >2 times the ULN or INR >1.5, without initial findings of cholestasis (elevated serum liver alkaline phosphatase isoenzyme)

10.4. Acute Kidney Injury

The Kidney Disease: Improving-Global Outcomes (KDIGO) guidelines for diagnosing AKI are:

- Increased serum creatinine ≥ 0.3 mg/dL (≥ 26.5 $\mu\text{mol/L}$) within 48 hours; or
- Increased serum creatinine ≥ 1.5 times baseline (that is known or presumed to have occurred within the prior 7 days); or
- Urine volume < 0.5 mL/kg/hour for 6 hours or more ([KDIGO 2013](#)).

These KDIGO guidelines typically apply to hospital settings, where baseline values within given timeframes (ie, the preceding 48 hours to 7 days) are available. However, in interventional trials such as the current study, values this recent will not likely be available in most cases. In such instances, at the Investigator's discretion, diagnosis of AKI may be based on the most recently available serum creatinine level preceding the event, provided this creatinine measurement was

conducted at or after the last study visit prior to the event (ie, was within 3 months prior to the event).

The Investigator should always take into consideration whether the event is true acute deterioration of kidney function due to an identified etiology, or whether the event represents natural progression of the underlying kidney disease. In cases of AKI where an etiology is identified, the reported AE term should reflect the etiology for the impairment of renal function (eg, AKI due to hypovolemia).

10.5. Serious Renal Conditions

The following conditions should always be reported as SAEs:

- Progression of CKD leading to chronic dialysis: For patients who undergo transition to chronic maintenance dialysis, the verbatim SAE term should be reported as “progression of CKD leading to chronic dialysis.” The term “chronic dialysis” should also be captured on the Concomitant Procedure page of the eCRF.
- Medical conditions requiring transient acute dialysis: For patients who undergo transient acute dialysis, the verbatim SAE term should record the condition for which the dialysis is required. For example, if a patient requires acute dialysis due to hyperkalemia, the verbatim SAE term would be reported as “hyperkalemia requiring transient acute dialysis.” The “acute dialysis” should also be captured on the Concomitant Procedure page of the eCRF.
- Kidney transplantation: For patients receiving a kidney transplant, the reason for the transplant should be recorded as the verbatim SAE (eg, “progression of CKD requiring kidney transplant”). The term “kidney transplant” should also be captured on the Concomitant Procedure page of the eCRF.

10.6. Evaluation of Adverse Events/Serious Adverse Events

10.6.1. Causality Assessment

Assessment of the relationship between the AE and exposure to the study medication is important for regulatory reporting and assists in the overall analysis of the safety information. For each AE/SAE the Investigator will determine whether, based on available evidence, there is a reasonable possibility that the study medication caused the event. Causal relationship will be classified according to the following criteria:

- Not Related: There is no suspicion of a causal relationship between exposure and the AE.
- Unlikely Related: There is no evidence for a causal relationship between exposure and the AE; however, such a relationship cannot be ruled out.
- Possibly Related: There is some evidence supporting the possibility of a causal relationship between exposure and the AE.
- Related: There is strong evidence that there is a causal relationship between exposure and the AE.

A causality assessment will be provided for each AE/SAE recorded, even if there is only limited information at the time.

Upon receipt of follow-up information, the Investigator may change their assessment of causality and amend the AE/SAE report accordingly.

10.6.2. Severity

Severity indicates the intensity of the event and should not be confused with seriousness (ie, [Section 10.2](#)), which is an event outcome applied for the purpose of event classification and regulatory reporting.

The Investigator will assess the severity of all AEs/SAEs as mild, moderate, or severe, based on the following definitions.

- Mild: A type of AE that is usually transient and may require only minimal treatment or therapeutic intervention. The event does not generally interfere with usual activities of daily living.
- Moderate: A type of AE that is usually alleviated with additional specific therapeutic intervention. The event interferes with usual activities of daily living, causing discomfort, but poses no significant or permanent risk of harm to the research patient.
- Severe: A type of AE that interrupts usual activities of daily living, or significantly affects clinical status, or may require intensive therapeutic intervention.

10.6.3. Outcome

Outcome describes the status of the AE. The Investigator will provide information regarding the patient outcome of each AE. Definitions for possible results of an AE outcome include:

- Recovered/Resolved: The event has improved, or the patient recuperated.
- Recovering/Resolving: The event is improving.
- Not Recovered/Not Resolved: The event has not improved, or the patient has not recuperated.
- Recovered/Resolved with sequelae: The patient recuperated but retained pathological conditions directly resulting from the disease or injury.
- Fatal: Termination of life as a result of an AE. There should be only 1 AE marked with this outcome.
- Unknown: Not known, not observed, not recorded, or refused.

10.6.4. Action Taken Regarding the Study Medication

The action taken with regard to the study medication in response to the AE will be provided at the time the event is reported. Options for action taken include the following:

- Drug Withdrawn: Medication schedule was modified by permanently terminating a prescribed regimen of medication.

- Dose Reduced: Medication schedule was modified by subtraction, either by changing the frequency, strength or amount.
- Dose Increased: Medication schedule was modified by addition; either by changing the frequency, strength or amount.
- Dose Not Changed: Medication schedule was maintained.
- Drug Interrupted: Medication schedule was modified by temporarily terminating a prescribed regimen of medication.
- Unknown: Not known, not observed, not recorded or refused.
- Not Applicable: Determination of a value is not relevant in the current context, for example, if the AE began and ended prior to treatment or after discontinuation of treatment.

10.6.5. Assessment of Expectedness

The expectedness of an SAE will be determined by the Sponsor in accordance with the sparsentan Reference Safety Information (which is contained in the [Investigator's Brochure](#)) or the irbesartan product label, as applicable.

10.7. Reporting Adverse Events and Serious Adverse Events

10.7.1. Reporting Adverse Events

Adverse events (including SAEs) will be captured from the time informed consent is signed to the patient's final visit.

For patients who prematurely discontinue study treatment (see [Section 8.3.2](#)) but who are not withdrawn from the study, AEs will continue to be recorded until the patient completes the study (see [Section 6.3.1](#) for definition of patient completion).

If a patient initiates RRT after premature discontinuation of study treatment, only AEs and SAEs considered related or possibly related to study treatment need to be recorded.

Adverse events will be recorded using appropriate medical terminology. When recording, it is preferable to provide a diagnosis. In the absence of a diagnosis, each sign and symptom will be captured as a unique AE. Sufficient information should be sought to assist the Investigator both in determining the diagnosis and in making a causality assessment.

Reporting should not be delayed pending receipt of all required information. If information is unavailable at the time of the initial report, the Investigator is expected to follow-up until the required information has been obtained.

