10.7.2. Reporting Serious Adverse Events

The necessity and time requirements for reporting of SAEs to the Sponsor or its designee and/or regulatory agencies are as follows:

- All SAEs will be reported by email to the SAE contact on the [Study Contact Information](#) page of this protocol or by fax to the number in the Investigator Site File

- within 24 hours of the Investigator's first knowledge of the event, regardless of causal relationship.
- For the double-blind portion of the study (Day 1 through Week 112) and the open-label extension portion of the study (Week 112 and after), a completed SAE Report Form containing a detailed written description of the event along with available supporting documents (eg, discharge summary, autopsy report, diagnostic test results, etc.) will be provided by email to the SAE contact on the [Study Contact Information](#) page or by fax to the number in the Investigator Site File. For complete instructions, refer to SAE Report Form completion guidelines.
 - Additional information that is not available at the time the initial SAE Report Form was completed will be promptly reviewed and provided by email to the SAE contact on the Study Contact Information page or by fax to the number in the Investigator Site File within 48 hours of receipt. Full supporting documentation should be solicited by the investigative site even if the SAE occurred at another institution. Such documentation may include copies of relevant patient/hospital records, discharge summaries, laboratory/test results or autopsy reports.
 - If at any time after the patient has completed participation in the study (as defined in [Section 6.3.1](#) and [Section 6.3.2](#)), the Investigator or study staff becomes aware of an SAE that they suspect is related to the study medication (see [Section 10.6.1](#)), the event and any known details will be reported promptly by email to the SAE contact on the Study Contact Information page or by fax to the number in the Investigator Site File, following the reporting instructions in this section.

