10. SAFETY AND TOLERABILITY

Safety analyses will be conducted using the Safety Analysis Set at both interim and final analysis. At the interim analysis, all available data will be summarized. Unless otherwise noted, all safety analyses will be conducted using on-study data. All safety analyses specified below refer to the double-blind period only, except where noted. If >5% of patients initiate RRT while on study, select summaries excluding results after initiation of RRT may be prepared.

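### Protocol 10.7.1 lets sites omit unrelated SAEs once an off-drug patient starts renal replacement therapy, in conflict with 10.5 and 10.7.2, and the SAP does not mention the filter

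*Protocol*

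**What the plan says.** Protocol 10.7.1 opens with a general rule: "Adverse events (including SAEs) will be captured from the time informed consent is signed to the patient's final visit". For patients who stop treatment early but stay in the study, it adds that "AEs will continue to be recorded until the patient completes the study". It then makes an exception: "If a patient initiates RRT after premature discontinuation of study treatment, only AEs and SAEs considered related or possibly related" to study treatment have to be recorded.

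Protocol 10.7.2 requires all SAEs to be sent within 24 hours of the investigator's "first knowledge of the event, regardless of causal relationship". Protocol 10.5 is equally general: "The following conditions should always be reported as SAEs". Its list covers progression to chronic dialysis, conditions that need transient acute dialysis, and kidney transplantation.

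SAP 10 sets the default data basis: "Unless otherwise noted, all safety analyses will be conducted using on-study data". Its only provision for RRT is that, if more than 5% of patients start RRT on study, "select summaries excluding results after initiation of RRT may be prepared". SAP 10.1 describes AE collection as running from consent until the patient has finished the study, with no RRT exception.

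**The concern.** The exception names SAEs, so it cannot be read as relief from recording minor events only. It gives the site a lower standard for the same events that 10.5 and 10.7.2 treat as mandatory, and nothing in the protocol says which section prevails.

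Protocol 6.4.2 encourages off-drug patients to keep attending visits to Week 112, partly so that safety data can still be collected. The exception cuts across that purpose. It is triggered by RRT, which happens after randomisation and which a nephroprotective drug is meant to make less frequent. What is captured after that point depends on each investigator's view of causality. If RRT after drug stop differs between arms, completeness of SAE recording can differ between arms too. Both the on-study safety tables and the SAE list reviewed by the DMC (Protocol 13.2) are presented as if collection were complete.

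**Working it through.** The documents give no figure to reproduce, so the check is to trace the same event through each section.

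1. **Unrelated SAE (for example, a hospitalisation) in an off-drug patient already on RRT.** Under 10.7.1, recording is optional. Under 10.7.2, reporting is mandatory within 24 hours. No cross-reference links the two.

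2. **Later kidney transplant in that patient, judged unrelated to drug.** Under 10.7.1, recording as an SAE is optional. Under 10.5 it is mandatory, and under 10.7.2 it is mandatory as an SAE. SAP 8.8.4 also expects RRT, including transplant, on the Adverse Events eCRF as well as the Concomitant Procedures eCRF.

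3. **The same events in a patient whose drug was stopped because RRT began.** Protocol 6.4.2 lists RRT or transplant as a reason for permanent discontinuation. The exception is worded for RRT that follows discontinuation, so it does not clearly apply here, and the full rules stand. Two clinically similar patients can be recorded to different standards because of the order of two dates.

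4. **Where 10.7.2 itself uses a causality filter.** It does so only for SAEs that a site learns of after the patient has completed participation. A patient on RRT who is still attending visits has not reached that point, so 10.7.2 gives the exception no support.

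5. **What the SAP assumes.** Serious TEAEs are tabulated by system organ class and preferred term on on-study data. The optional summaries leave out results after RRT. The SAP nowhere says that the post-RRT results in its main tables may already be filtered by causality.

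6. **Size.** The one relevant number is the SAP trigger: 0.05 × 300 = 15, so more than 15 patients would have to start RRT before the optional summaries are considered. This counts any RRT on study. The documents give no expected RRT rate, no rate of RRT after drug stop, no remaining follow-up time and no SAE rate on dialysis. The number of events that could go unrecorded cannot be calculated.

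**The case against.** Several points on the other side stand.

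- **The exception sets a minimum.** It says what needs to be recorded and forbids nothing. A site that reports every SAE under 10.7.2 and every transplant under 10.5 breaches no rule. A reader might infer that unrelated SAEs never reach the sponsor or the DMC. The text supports only that they may not, depending on which section the site follows.
- **It may be deliberate.** A specific exception can override a general rule. But 10.5 and 10.7.2 are written without limits, and neither they nor the SAP acknowledges it.
- **The renal outcome itself is not lost.** Protocol 10.5 and SAP 8.8.4 put chronic dialysis and transplant on the Concomitant Procedures eCRF. Death is a reason for leaving the study (Protocol 6.5), and that reason goes on the End of Study eCRF. The 30% and 40% eGFR, ESRD or death composites are therefore largely protected.
- **The on-treatment safety summaries are largely untouched.** For patients who discontinue, SAP 10.1.3 closes the window 30 days after last dose, so the filter matters there only if RRT starts within those 30 days. The general on-study table of serious TEAEs has no such protection.
- **No imbalance is shown.** A reader might infer that the rule flatters sparsentan. The documents do not support that. If RRT after drug stop were more common on irbesartan, the losses would fall mainly in the control arm and make sparsentan look relatively worse.

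**Conclusion.** The conflict is real and can be read directly from the text. For an off-drug patient who starts RRT, 10.7.1 makes unrelated SAEs optional, while 10.7.2 and 10.5 make them mandatory, and the SAP is written as if no filter existed. The possible harm is incomplete SAE data after RRT, in the on-study tables and in what the DMC sees. Completeness would then depend on a post-randomisation outcome and on causality opinion.

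Its size is unknown. It is tempting to take the SAP's 5% trigger as an expected rate and multiply it into a count of lost SAEs. That does not work: the trigger is a reporting threshold for any RRT, not a forecast, and it does not refer to the narrower group who stop drug first. Nor do the documents support stating that SAE counts will fail to be comparable between arms; they show only how that could happen.

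The primary eGFR slope analysis uses on-treatment assessments (SAP 8.5.1) and is not affected. This is a safety-data correction that should be made because it is cheap and removes a plain contradiction.

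**What to change.** In Protocol 10.7.1, delete the reference to SAEs from the RRT exception. All SAEs would then be recorded whatever their cause, through Week 112, in every patient still followed, in line with 10.5 and 10.7.2. Any reduced collection after RRT would cover non-serious AEs only.

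In SAP 10, state that non-serious AE data after RRT in patients already off drug are filtered by causality, and that the on-study AE tables should be interpreted accordingly.

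There is no need to extend reduced collection to every RRT start or to make AE follow-up end at RRT. The first would discard data now required, and the second would truncate follow-up on the same post-randomisation event.

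The cost is two words in the protocol, a short statement in the SAP, and a few more SAE forms for dialysis or transplant patients.

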10.7.2. Reporting Serious Adverse Events

The necessity and time requirements for reporting of SAEs to the Sponsor or its designee and/or regulatory agencies are as follows:

- All SAEs will be reported by email to the SAE contact on the [Study Contact Information](#) page of this protocol or by fax to the number in the Investigator Site File

- within 24 hours of the Investigator's first knowledge of the event, regardless of causal relationship.
- For the double-blind portion of the study (Day 1 through Week 112) and the open-label extension portion of the study (Week 112 and after), a completed SAE Report Form containing a detailed written description of the event along with available supporting documents (eg, discharge summary, autopsy report, diagnostic test results, etc.) will be provided by email to the SAE contact on the [Study Contact Information](#) page or by fax to the number in the Investigator Site File. For complete instructions, refer to SAE Report Form completion guidelines.
 - Additional information that is not available at the time the initial SAE Report Form was completed will be promptly reviewed and provided by email to the SAE contact on the Study Contact Information page or by fax to the number in the Investigator Site File within 48 hours of receipt. Full supporting documentation should be solicited by the investigative site even if the SAE occurred at another institution. Such documentation may include copies of relevant patient/hospital records, discharge summaries, laboratory/test results or autopsy reports.
 - If at any time after the patient has completed participation in the study (as defined in [Section 6.3.1](#) and [Section 6.3.2](#)), the Investigator or study staff becomes aware of an SAE that they suspect is related to the study medication (see [Section 10.6.1](#)), the event and any known details will be reported promptly by email to the SAE contact on the Study Contact Information page or by fax to the number in the Investigator Site File, following the reporting instructions in this section.

10.7.3. Follow-up of Adverse Events and Serious Adverse Events

All AEs will be followed until resolution, until the condition stabilizes, or until completion of the patient's participation or study termination, whichever occurs first.

Serious AEs will be followed until resolution, until the condition stabilizes, or until the Investigator and the Sponsor agree that follow-up is no longer necessary.

All AEs/SAEs documented at a previous visit/contact where event outcome is designated as not recovered/not resolved, recovering/resolving or unknown will be reviewed by the Investigator at subsequent visits/contacts. SAEs that are ongoing after completion of the last scheduled visit will continue to be followed to determine the final outcome.

Rules for AE/SAE follow-up apply to all patients, to the extent allowed by the patient's consent. The Investigator will ensure that follow-up includes further investigations consistent with appropriate medical management to understand the nature and/or causality of the AE/SAE. The Sponsor, its designee, or regulatory authorities may also request additional information regarding an SAE at any time.

All follow-up information will be promptly reviewed by the Investigator and provided by email to the SAE contact on the Study Contact Information page of this protocol or by fax to the number in the Investigator Site File within the specified timelines. Additional AEs/SAEs may be identified during the review of follow-up information and will be processed in accordance with requirements defined throughout [Section 10](#).

10.7.4. Reporting to Regulatory Authorities, Investigators and Institutional Review Boards/Independent Ethics Committees

The Sponsor will ensure that processes are in place for provision of SAEs and Expedited SAE reports (SUSARs) to Regulatory Authorities, Investigators, and Institutional Review Boards (IRBs)/Independent Ethics Committees (IECs) as required, within the specified timelines.

The Sponsor will submit SAE and/or SUSAR reports to regulatory authorities and the Investigator as required. In the US, Investigators will report SAEs and SUSARs to their IRB in accordance with applicable SOPs and/or local reporting requirements. In Europe, the Sponsor or its designee will notify the IEC of any SUSARs. In regions/countries other than the US/Europe, reporting of events to IECs or local authorities will be performed by the Investigator/Sponsor or its designee and will be done in accordance with local procedures/regulations.

Investigators will forward copies of the IRB/IEC notification to the Sponsor or its designee, when applicable.

